### **Intra-patient dose escalation**

Intra-patient dose escalations for CB-103 must be approved by the Sponsor and will be only allowed on a case-by-case basis, upon evaluation and discussion between the Investigator and the Sponsor. The following criteria have to be fulfilled for a patient under consideration:

- Intra-patient dose escalation can occur only when the next higher dose has been cleared by the CRC. Additional safety data collected will not be included in DLT assessment and discussions for dose escalation.
- Intra-patient dose escalation will be implemented on the first day of the cycle.

## **7.4.6 Follow-up for Dose-Limiting Toxicities**

Patients whose treatment is interrupted or permanently discontinued due to an adverse event or clinically significant laboratory value, must be followed at least once a week for 4 weeks, and subsequently at 4-week intervals, until resolution or stabilisation of the event, whichever comes first.

### **7.4.6.1 Follow-up Evaluations and Dosing Modifications for Toxicities**

The follow-up evaluations for toxicities apply during or beyond cycle 1 in Part A, and throughout Part B of the study.

The following sections outline the specific dose modifications for CB-103 for haematologic and non-haematologic toxicities and should be followed by the Investigator accordingly.

#### **7.4.6.1.1 Haematologic Toxicities for Solid Tumour Patients**

If  $\geq$  CTCAE grade 3 neutropenia or  $\geq$  CTCAE grade 3 thrombocytopenia have been demonstrated, testing for these parameters must be repeated at least twice a week until resolution to  $\leq$  CTCAE grade 1 neutropenia or  $\leq$  CTCAE grade 1 thrombocytopenia, to allow for re-treatment and then at least weekly until either resolution or until stabilisation.

**Table 4** Dose modifications for haematologic toxicities

Dose Modifications for CB-103	
Worst Toxicity CTCAE Grade unless otherwise specified (Value)	At any time during a cycle of CB-103 (including intended day of dosing)
Haematologic toxicities:	
Neutropenia (ANC)	
Grade 1 (ANC < LLN - 1.5 x 10  /L) & Grade 2 (ANC < 1.5 - 1.0 x 10  /L)	Maintain dose level
Grade 3 (ANC < 1.0 - 0.5 x 10  /L)	Omit dose administration until resolved to ≤ grade 1, 
 
• If resolved in ≤ 7 days, then maintain dose level
 
• If resolved in > 7 days, then ↓ 1 dose level
 

Grade 4 (ANC < 0.5 x 10  /L)	Omit dose administration until resolved to ≤ grade 1, then ↓ 1 dose level
Grade 3 Febrile neutropenia (ANC < 1.0 x 10  /L with a single temperature of >38.3°C or a sustained temperature of ≥38°C for more than one hour)	Omit dose administration until resolved, then ↓ 1 dose level
Thrombocytopenia	
Grade 1 (PLT < LLN - 75 x 10  /L)	Maintain dose level
Grade 2 (PLT < 75 - 50 x 10  /L) & Grade 3 (PLT < 50-25 x 10  /L)	Omit administration dose until resolved to ≤ grade 1, then: 
 
• If resolved in ≤ 7 days, then maintain dose level
 
• If resolved in > 7 days, then ↓ 1 dose level
 

Grade 4 (PLT < 25 x 10  /L)	Omit administration dose until resolved, then ↓ 1 dose level

 Common Terminology Criteria for Adverse Events (CTCAE Version 4.03)

#### 7.4.6.1.2 Renal Toxicities

If serum creatinine ≥ 2 x ULN has been demonstrated, this parameter must be repeated at least twice a week until resolution to ≤ CTCAE grade 1, to allow for initiation of re-treatment and then at least weekly until either resolution or until stabilisation.

If proteinuria or haematuria ≥ CTCAE grade 2 or serum creatinine ≥ 2.0 x ULN has been demonstrated, a 24-hour urine collection must be obtained for total protein and total creatinine must be repeated at least weekly until either resolution to baseline value to allow for initiation of re-treatment, or until stabilisation. Whenever a measured CrCl is obtained, a serum creatinine value should be obtained within ≤ 72 hours of the urine collection.

**Table 5** Dose modifications for renal toxicities

Dose Modifications for CB-103	
Worst Toxicity CTCAE Grade unless otherwise specified (Value)	At any time during a cycle of CB-103 (including intended day of dosing)
Renal toxicities:	
Serum creatinine	
(< 2 x ULN)	Maintain dose level
(2 - 3 x ULN)	Omit dose administration until resolved to ≤ grade 1, 
 
• If resolved in ≤ 7 days, then maintain dose level
 
• If resolved in > 7 days, then ↓ 1 dose level
 

Grade 3 (> 3.0 - 6.0 x ULN) & Grade 4 (> 6.0 x ULN)	Omit dose administration and discontinue patient from study treatment

 Common Terminology Criteria for Adverse Events (CTCAE Version 4.03)

#### **7.4.6.1.3 Hepatic Toxicities**

If bilirubin ≥ CTCAE grade 2 or AST/ALT ≥ CTCAE grade 3 has been demonstrated, these parameters must be repeated at least twice a week until resolution to ≤ CTCAE grade 1 (or baseline if liver metastases were present at baseline), to allow for initiation of re-treatment and then at least weekly until either resolution or until stabilisation.

Patients with total bilirubin > ULN (any duration) should have fractionation of bilirubin into total/direct or indirect/direct components and any additional work-up as clinically indicated by these results. Follow-up of hyperbilirubinaemia should proceed as per the guidelines above, irrespective of the results of fractionation.

**Table 6** Dose modifications for hepatic toxicities

Dose Modifications for CB-103	
Worst Toxicity CTCAE Grade unless otherwise specified (Value)	At any time during a cycle of CB-103 (including intended day of dosing)
Hepatic toxicities:	
Bilirubin	
Grade 1 (< 1.5 x ULN)	Maintain dose level
Grade 2 (1.5 - 3 x ULN)	Omit dose administration until resolved to ≤ grade 1, 
 
• If resolved in ≤ 7 days, then maintain dose level
 
• If resolved in > 7 days, then ↓ 1 dose level
 

Grade 3 (> 3.0 - 10.0 x ULN)	Omit dose administration until resolved to ≤ grade 1, then ↓ 1 dose level
Grade 4 (> 10.0 x ULN)	Omit dose administration and discontinue patient from study treatment
AST or ALT	
Grade 1 (> ULN – 3.0 x ULN) & Grade 2 (>3.0 - 5.0 x ULN) without increase in total bilirubin >2 x ULN	Maintain dose level
Grade 3 (> 5.0 - 20.0 x ULN) without increase in total bilirubin >2 x ULN	Omit dose administration until resolved to ≤ grade 1 (or ≤ grade 2 in case of liver metastasis), then 
 
• If resolved in ≤ 7 days, then maintain dose level
 
• If resolved in > 7 days, then ↓ 1 dose level
 

Grade 4 (> 20.0 x ULN) without increase in total bilirubin >2 x ULN	Omit dose administration until resolved to ≤ grade 1, then ↓ 1 dose level

 Common Terminology Criteria for Adverse Events (CTCAE Version 4.03)

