## 3. Organ function and laboratory results

Patients must have the following laboratory values (obtained within 14 days of enrolment):

- a. Total serum bilirubin  $\leq 1.5$  x upper limit of normal (ULN)
- b. Alkaline phosphatase (ALP)  $\leq 2.5$  x ULN; if liver function abnormalities are due to the underlying malignancy and known bone metastases, then ALP must be  $\leq 5$  x ULN

- c. Serum aspartate aminotransferase (AST/SGOT) and alanine aminotransferase (ALT/SGPT)  $\leq 2.5 \times \text{ULN}$ ; if liver function abnormalities are due to the underlying malignancy and known hepatic metastases or bone metastases, then AST and ALT must be  $\leq 5 \times \text{ULN}$
- d. Serum creatinine  $\leq 1.5 \times \text{ULN}$ ; or if serum creatinine  $> 1.5 \times \text{ULN}$ , then serum creatinine clearance (CrCl)  $\geq 50 \text{ mL/min}$  (estimated by Cockcroft-Gault formula)
- e. Potassium levels within normal limits or correctable with supplements
- f. Total calcium levels (corrected for serum albumin) within normal limits or correctable with supplements
- g. Magnesium levels within normal limits or correctable with supplements
- h. Phosphorus levels within normal limits or correctable with supplements
- i. Serum albumin concentration  $\geq 30 \text{ g/L}$
- j. Patients with solid tumours must have:
  - Absolute neutrophil count (ANC)  $\geq 1.5 \times 10^9/\text{L}$
  - Haemoglobin (Hgb)  $\geq 10 \text{ g/dL}$  ( $\geq 100 \text{ g/L}$ )
  - Platelet count  $\geq 75 \times 10^9/\text{L}$  (without platelet transfusion or growth factor support in the preceding 7 days)
  - Partial thromboplastin time (PTT)  $\leq 1.5 \times \text{ULN}$  and international normalised ratio (INR)  $\leq 1.3$  (unless the patient is receiving therapeutic anticoagulants)

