### 3. Organ function and laboratory results

Patients must have the following laboratory values (obtained within 14 days of enrolment):

- a. Total serum bilirubin  $\leq 1.5 \times$  upper limit of normal (ULN)
- b. Alkaline phosphatase (ALP)  $\leq 2.5 \times$  ULN; if liver function abnormalities are due to the underlying malignancy and known bone metastases, then ALP must be  $\leq 5 \times$  ULN
- c. Serum aspartate aminotransferase (AST/SGOT) and alanine aminotransferase (ALT/SGPT)  $\leq 2.5 \times$  ULN; if liver function abnormalities are due to the underlying malignancy and known hepatic metastases, then AST and ALT must be  $\leq 5 \times$  ULN
- d. Serum creatinine  $\leq 1.5 \times$  ULN; or if serum creatinine  $> 1.5 \times$  ULN, then serum creatinine clearance (CrCl)  $\geq 50$  mL/min (estimated by Cockcroft-Gault formula)
- e. Potassium levels within normal limits or correctable with supplements
- f. Total calcium levels (corrected for serum albumin) within normal limits or correctable with supplements
- g. Magnesium levels within normal limits or correctable with supplements
- h. Phosphorus levels within normal limits or correctable with supplements
- i. Serum albumin concentration  $\geq 30$  g/L
- j. Patients with solid tumours must have:
  - Absolute neutrophil count (ANC)  $\geq 1.5 \times 10^9/L$
  - Haemoglobin (Hgb)  $\geq 10$  g/dL ( $\geq 100$  g/L)
  - Platelet count  $\geq 75 \times 10^9/L$  (without platelet transfusion or growth factor support in the preceding 7 days)
  - Partial thromboplastin time (PTT)  $\leq 1.5 \times$  ULN and international normalised ratio (INR)  $\leq 1.3$  (unless the patient is receiving therapeutic anticoagulants)

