#### **7.4.5 Dose Modifications, Dose Delays and Treatment Discontinuation**

Every effort should be made to administer CB-103 at the planned dose and schedule. In the event of treatment-related toxicities and DLT with CB-103, dose or schedule adjustments are required and have to be undertaken by the Investigator in the best interest of the patient to continue therapy. In the event of multiple toxicities, the dose modification should be based on the worst toxicity observed (according to the NCI CTCAE, v4.03). Any adjustment to the CB-103 dose should be documented in the eCRF.

Dose adjustments and interruptions criteria are described in the following sections. Depending on the type, severity and timing of the events, the Investigator will determine and decide on dose reductions and resumption of treatment. The following rules have to be followed:

- After Cycle 1 / Day 1, a continuous treatment interruption of more than 14 days will result in discontinuation of the patient from the study. Interruption of treatment not related to CB-103 may not require discontinuation; in such a case treatment continuation must be discussed with the Sponsor.
- Patients with a continuous treatment delay for more than 7 days during cycle 1 in Part A of the study (DLT period) that is not due to a drug-related AE, will be considered non-evaluable for DLT and will need to be replaced accordingly.
- Doses of CB-103 held or missed will not be made up (i.e., cycles will not be prolonged beyond the 28th calendar day in order to make up any missed doses).
- If doses of CB-103 are missed or forgotten to be taken for more than three sequential dosing events and if this happens more than once, this will result in discontinuation of the patient from the study. Dose delays as outlined above to recover from adverse events are allowed.
- If a treatment interruption continues beyond Day 28 of the current cycle, then the day when treatment is restarted will be counted as Day 1 of the next cycle.
- During cycle 1 in Part A (DLT period), any dose adjustments must be discussed with and approved by the Sponsor.
- One dose reduction is allowed per patient. In case the patient shows clinical benefit a 2nd dose reduction might be allowed, but this needs to be agreed upon on a case-by-case basis with the Sponsor. Section [7.4.6.1](#) describes the CB-103 dose modifications for the haematologic and non-haematologic toxicities not clearly attributed to disease.

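### For patients with liver metastases, the hepatic toxicity text and Table 6 of the protocol set different AST/ALT recovery thresholds for restarting CB-103

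*Protocol*

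**What the plan says.** Protocol 7.4.6.1.3 deals with AST/ALT of grade 3 or worse twice. The running text asks for retesting, twice weekly or more often, until the value is back to grade 1 or better, with the alternative "or baseline if liver metastases were present at baseline), to allow for initiation of re-treatment".

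Table 6, in the same section, sets conditions by grade. The AST/ALT Grade 3 row reads "Omit dose administration until resolved to ≤ grade 1 (or ≤ grade 2 in case of liver metastasis), then". A 7-day rule follows: the dose is kept if recovery took 7 days or less and drops one level if it took longer. The Grade 4 row holds dosing until grade 1 or better and then drops one level. It mentions neither baseline nor liver metastasis.

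Four other places bear on the point:

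- Section 6.1.1, inclusion criterion 3c, limits AST/ALT to 2.5 x ULN but relaxes this to 5 x ULN: "if liver function abnormalities are due to the underlying malignancy and known hepatic metastases, then AST and ALT must be" within that higher limit.
- The same criterion in the synopsis is wider: "known hepatic metastases or bone metastases, then AST and ALT must be" within 5 x ULN.
- Section 7.4.5 states that "a continuous treatment interruption of more than 14 days will result in discontinuation of the patient from the study". Interruptions unrelated to CB-103 may be discussed with the Sponsor.
- Section 7.4.6.1.2 (renal) uses grade 1 or better for creatinine in its first paragraph and in Table 5. Its second paragraph asks for repeats "until either resolution to baseline value to allow for initiation of re-treatment, or until stabilisation".

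**The concern.** A site managing a raised AST or ALT in a patient with liver metastases finds two answers in one section to the question of when dosing may resume. The answer also feeds two further rules. The 7-day rule in the Grade 3 row decides whether the dose is kept or lowered, and the 14-day rule in 7.4.5 decides whether the patient stays in the study.

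The affected patients are not marginal. Hepatic metastases are explicitly allowed for at entry, and 2.5.5.1 describes NOTCH1-mutant ACC as tending to liver and bone metastasis. Section 2.5.6 reports a related serious event of drug-induced liver injury in an ACC patient with extensive liver involvement. The conflict is therefore first a safety matter. It can also add variation between sites in dose level and discontinuation.

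**Working it through.** There is no planned figure to reproduce, so the check sets the rules side by side in multiples of ULN.

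**Inputs.** AST/ALT grades come from Table 6: grade 1 up to 3.0, grade 2 above 3.0 to 5.0, grade 3 above 5.0 to 20.0, grade 4 above 20.0. The Table 6 AST/ALT rows apply without bilirubin above 2 x ULN. Entry limits come from criterion 3c. Let b be the baseline value.

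**Highest value at which dosing may resume.**

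- Text, liver metastases at baseline: the larger of 3.0 and b, because baseline is an alternative to grade 1.
- Text, no liver metastases: 3.0.
- Table 6 after grade 3: 5.0 with liver metastasis, otherwise 3.0.
- Table 6 after grade 4: 3.0 for everyone.

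| Patient | Event | Text | Table 6 | Table minus text |
|---|---|---|---|---|
| No liver metastases | grade 3 or 4 | 3.0 | 3.0 | 0 |
| Liver metastases, b = 1.0 | grade 3 | 3.0 | 5.0 | +2.0 |
| Liver metastases, b = 1.0 | grade 4 | 3.0 | 3.0 | 0 |
| Liver metastases, b = 4.0 | grade 3 | 4.0 | 5.0 | +1.0 |
| Liver metastases, b = 4.0 | grade 4 | 4.0 | 3.0 | -1.0 |
| Bone metastases only, b = 4.0 (eligible under the synopsis only) | grade 3 or 4 | 3.0 | 3.0 | 0 |

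The table is looser than the text after grade 3 and stricter after grade 4 when baseline is grade 2. For an eligible grade 2 baseline (above 3.0 to 5.0), the Grade 4 row requires a fall of b - 3.0 below baseline, from just above 0 to 5.0 - 3.0 = 2.0 x ULN. In the last row text and table agree, but both sit 4.0 - 3.0 = 1.0 x ULN below baseline.

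**Effect on dose.** Take b = 1.0 with liver metastases, a grade 3 event, and 4.5 x ULN on day 6. Under Table 6, 4.5 is below 5.0, so dosing resumes at the same dose. Under the text, 4.5 exceeds 3.0, so the hold continues. If the first value at or below 3.0 comes after day 7 and recovery is counted by the text, the 7-day rule means one level lower. If it comes by day 7, only the restart day differs.

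**Effect on participation.** Take b = 4.0 with hepatic metastases, a grade 4 event, and a return to 4.0 on day 10 that then holds. Under the text, baseline is reached and dosing may resume. Under Table 6, 4.0 exceeds 3.0, so the hold continues past 14 days and 7.4.5 ends participation.

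**Precedence.** I found nothing saying whether text or table prevails. Section 7.4.6.1 tells the investigator to follow these sections. The most-conservative-approach rule in 7.4.5 covers only concurrent haematological and non-haematological toxicity.

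**Bilirubin.** The text offers the baseline alternative here too, and Table 6 does not. Entry is capped at 1.5 x ULN, so apart from that exact boundary it makes no practical difference.

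**Renal.** For creatinine of 2 x ULN or more, the first paragraph and Table 5 (its 2 - 3 x ULN row) agree on grade 1 or better. The second paragraph shares the creatinine trigger, adds proteinuria and haematuria, and ties re-treatment to baseline. Its sentence about the 24-hour urine collection is garbled, so baseline may refer to the urine measures.

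**The case against.** The strongest defence is that the scope is narrow. Without liver metastases there is no hepatic conflict. Different rows for grades 3 and 4 are severity tiers, and a stricter recovery after more than 20 x ULN may be deliberate. In Cycle 1, grade 4 AST/ALT is a DLT under the synopsis, and 9.2.4 lists a DLT as a reason for withdrawal, so a restart rule would seldom be reached. Section 7.4.5 also leaves resumption to the investigator and requires Sponsor approval of Cycle 1 dose adjustments.

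Much of this stands, and it confines the grade 4 conflict mainly to later cycles. It does not remove it. Section 7.4.6.1 applies these rules beyond Cycle 1 and throughout Part B, and 7.4.5 itself speaks of adjusting the dose after a DLT so that therapy can continue. Nor can intent be read from the Grade 4 row: Tables 7 and 9 write in a baseline alternative where they want one, but the running text of 7.4.6.1.3 grants it here.

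A reader might infer several stronger things that the documents do not support:

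- That patients entering with grade 2 transaminases can never restart. After grade 3, such a patient with liver metastases meets both rules on return to baseline. Only the Grade 4 row (or either rule, for bone-only patients admitted under the synopsis) lies below baseline, and values may fall below baseline.
- That the table allows up to five times what the text allows. The text accepts grade 1 or baseline, so the comparison is 5.0 against 3.0 x ULN.
- That one laboratory course can end in full dose, reduced dose or discontinuation. The two worked courses give two outcomes each, and after grade 4 Table 6 never keeps the dose.
- That Cycle 1 evaluability is lost. Missing the 75% dosing minimum because of an unresolved related event is itself a DLT, and patients with a DLT enter the dose-determining set.
- That the renal section has the same text-against-table split. It rests on one unclear paragraph.

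**Conclusion.** The contradiction is real and is confined to patients with liver metastases. After a grade 3 event, the table's ceiling exceeds the text's by up to 2.0 x ULN (baseline 3.0 x ULN or below). After a grade 4 event, it is lower by up to 2.0 x ULN (baseline 5 x ULN). The first can change the restart day and, depending on the values seen by day 7, the dose level. The second can decide between restart and discontinuation, mainly after Cycle 1.

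This rests on reading the text's baseline provision as an alternative to grade 1, and on an interruption attributed to CB-103. How many patients would be affected cannot be derived from the documents. The mismatch on bone metastases between the synopsis and 6.1.1 is a separate, definite inconsistency. The renal point is unclear wording that may amount to a conflict. Correction is warranted because the issue touches safety and needs only wording.

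**What to change.** - Reconcile the running text of 7.4.6.1.3 with the AST/ALT Grade 3 and Grade 4 rows of Table 6.
- Reconcile inclusion criterion 3c in the synopsis with 6.1.1 on bone metastases.
- In the second paragraph of 7.4.6.1.2, state which measurement must return to baseline, and reconcile it with the first paragraph and Table 5.

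Which threshold applies is the sponsor's clinical decision, and none is proposed here. The cost is protocol wording in the synopsis, one eligibility criterion, two toxicity sections and, depending on how they are reconciled, their tables. No new assessments are needed. The SAP refers to the protocol for guidance on dose reduction and resumption (SAP 2.1.4) and states no restart thresholds of its own, so it needs no change.

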#### 7.4.6.1.4 Ocular/Vision-related Toxicities

For toxicities related to visual symptoms related to CB-103, refer to the following table.

**Table 7** Dose modifications for ocular/vision-related toxicities

Dose Modifications for CB-103	
Worst Toxicity CTCAE Grade unless otherwise specified (Value)	At any time during a cycle of CB-103 (including intended day of dosing)
Visual symptoms	
Grade 1	Maintain dose level
Grade 2	Omit dose administration until resolved to $\leq$ grade 1 (or baseline), then continue treatment with CB-103 at the current dose level  If visual symptoms $\geq$ Grade 2 recur upon re-exposure to CB-103 and if is intolerable by patient, discontinue patient from study
Grade 3	Omit dose administration and discontinue patient from study
Grade 4	Omit dose administration and discontinue patient from study

 Common Terminology Criteria for Adverse Events (CTCAE Version 4.03)

#### 7.4.6.1.5 Cardiac Toxicities

As in non-clinical studies with CB-103, QT prolongation was observed at higher doses and ECG changes in patients may be observed, therefore, intensive cardiac monitoring is implemented into this study with central management and review of multiple ECGs and Holter ECGs at selected timepoints. Furthermore ECHO/MUGA scans and cardiac markers will be assessed at selected time points. For toxicities related to QTc prolongation, refer to [Table 8](#) below. For all other cardiac toxicities, please follow the non-laboratory recommendations seen in Section [7.4.6.1.7](#).

**Table 8** Dose modifications for cardiac toxicities

Dose Modifications for CB-103	
Worst Toxicity CTCAE Grade unless otherwise specified (Value)	At any time during a cycle of CB-103 (including intended day of dosing)
Cardiac - Prolonged QTcF interval	
During Cycle 1:	
Absolute QTcF < 480 ms	Maintain dose level and ECG monitoring as per visit schedule.

Dose Modifications for CB-103	
Worst Toxicity CTCAE Grade unless otherwise specified (Value)	At any time during a cycle of CB-103 (including intended day of dosing)
Cardiac - Prolonged QTcF interval	
QTcF $\geq$ 480 ms and $<$ 500 ms	Maintain dose level. ECG monitoring assessments should be increased as indicated (e.g. hourly until no QTcF $\geq$ 480 ms).
During any Cycle:	
Grade 3 or QTcF $\geq$ 500 ms as identified by the Investigator on the ECG.	
Omit dose administration. Monitor patient with frequent ECGs as indicated (e.g. hourly) until the QTcF has returned to <math>\leq</math> 480 ms. Further monitoring as clinically indicated. Exclude other causes of QTc prolongation such as hypokalaemia, hypo-magnesaemia and blood oxygenation status. Once QTcF prolongation has resolved, and if the QTcF prolongation was confirmed by central reading, patients may be re-treated at one lower dose level at the Investigator's discretion.
 
ECG monitoring must continue throughout the treatment period as follows:
 
 
• ECG monitoring assessments should be performed for 2 additional cycles at higher frequency as clinically indicated
 
• If the ECGs obtained in the first additional cycle after dose reduction are without any QTcF prolongation, then ECG monitoring in subsequent cycles will be continued as per the visit schedule.
 
• If the patient had an absolute QTcF <math>\geq</math> 480 ms and <math><</math> 500 ms, then ECG monitoring at a higher frequency will be continued for all subsequent cycles.
 
• Patients who experience absolute QTcF <math>\geq</math> 500 ms after one dose reduction will be discontinued from study.
 
 
Note:
 
 
• If QTcF <math>\geq</math> 500 ms result is observed in a patient during the study treatment, this event will be considered as a DLT. If Torsades de Pointes are observed in a patient, the patient will be discontinued from the study.
 
• Whenever QTcF <math>\geq</math> 500 ms result is observed, a plasma sample for determination of CB-103 concentration should be obtained and the time of sample collection noted.
 

 Common Terminology Criteria for Adverse Events (CTCAE Version 4.03)

 Exclude other causes of QTcF prolongation such as hypokalaemia, hypomagnesaemia and blood oxygenation status. Patients who develop hypokalaemia or hypomagnesaemia during the study should receive electrolyte replacement as soon as possible and should not receive further CB-103 dosing until the respective electrolytes are documented to be within normal limits.

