#### **7.4.4 Dose-Limiting Toxicity (DLT)**

DLT is defined as an adverse event or abnormal laboratory value assessed as unrelated to disease progression, inter-current illness, or concomitant medications, that occurs  $\leq$  28 days following the first dose of CB-103 (Cycle 1) and that meets any of the following criteria shown in the table below. Clinically relevant toxicities will be evaluated according to the National Cancer Institute (NCI)/National Institutes of Health (NIH) CTCAE version 4.03.

For the purpose of dose-escalation decisions, only DLTs occurring during the first cycle of treatment will be necessarily considered in the binary logistic regression model.

Refer to the study synopsis “Dose limiting Toxicity” section for the DLTs criteria.

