**9.2.4 Criteria for Withdrawal from the Study**

Patients will be withdrawn from the study if the following criteria are met:

- Unequivocal disease progression
- Death
- Intervening illness that prevents further administration of treatment
- Unacceptable adverse events
- Intercurrent cardiac disease, especially drop in LVEF < 40% or drop > 15% from baseline (if LVEF with > 15% drop is still > 55% a second measurement after 1 week would be allowed before discontinuing the patient)
- Intercurrent interstitial lung disease or pneumonitis
- Patient non-compliance
- Pregnancy
- The patient decides to withdraw from study or is lost to follow-up
- General or specific changes in the patient's condition that render the patient not eligible for further treatment in the judgment of the Investigator
- If a patient experiences a DLT
- If a patient requires a continuous dose delay of more than 14 days (Part A and Part B) from the intended day of the next scheduled dose of CB-103
- If a patient is non-compliant and misses or forgets more than 3 sequential dosings on more than 1 occasion

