### **2.1.3 Planned Dose-Cohorts for Dose Escalation**

For Part A, the DLT period is defined as the 1st cycle of CB-103 dosing with a duration of 28 days. Eight provisional dose levels are defined for the dose escalation as well as one dose level with a 30% lower dose than the 1st dose level if the first dose level is not well tolerated.

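### Protocol Section 9.2.4 withdraws a patient for any DLT, while Section 7.4.5 and Tables 4, 5, 6, 8 and 9 allow re-treatment after the same events; the Table 8 Note also sets no cycle limit on QTcF DLTs

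*Protocol*

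**What the plan says.** **Withdrawal.** Protocol Section 9.2.4 gives a mandatory list of reasons for taking a patient off study. One entry is "If a patient experiences a DLT", with no exception.

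**Dose modification.** Section 7.4.5 calls for dose or schedule adjustment after a DLT so that the patient can stay on therapy. SAP 2.1.4 permits the same. The tables that carry this out sit under Section 7.4.6, whose title concerns follow-up of DLTs. Section 7.4.6.1 sets their reach: "The follow-up evaluations for toxicities apply during or beyond cycle 1 in Part A, and throughout Part B of the study".

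**QTcF.** In Table 8 (Section 7.4.6.1.5) the row for grade 3 or QTcF of 500 ms or more stands under "During any Cycle". Once the prolongation has resolved, and if central reading confirmed it, "patients may be re-treated at one lower dose level" at the investigator's discretion. Patients who again reach an absolute QTcF of at least "500 ms after one dose reduction will be discontinued from study". The Note in the same row says of QTcF of 500 ms or more: "result is observed in a patient during the study treatment, this event will be considered as a DLT".

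**DLT window.** Section 7.4.4 and the synopsis define a DLT as an event within "28 days following the first dose of CB-103 (Cycle 1) and that meets any of the following criteria shown in the table below". SAP 2.1.3 agrees: "the DLT period is defined as the 1st cycle of CB-103 dosing with a duration of 28 days". SAP 2.5 defines the DLT endpoint over the same first 28-day cycle.

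**The concern.** A site whose patient has a DLT finds two instructions, withdraw or hold and resume, for one patient and one event. This is a first-in-human study. A patient could be re-exposed to the drug when the withdrawal list says to stop, or taken off study when the dose-modification table would allow continuation.

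The cardiac case deserves most care. Section 2.5.2.1 reports QTc and QRS prolongation in dogs at the higher doses, and Section 3.2 accepts a possible effect on cardiac repolarisation and conduction. For QTcF of 500 ms or more there is a second difficulty. The Note calls the event a DLT at any time on treatment, although the DLT definition stops at day 28. It is then unclear whether an event in, say, Cycle 4 leads to withdrawal under Section 9.2.4 or to dose reduction under Table 8.

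**Working it through.** This is a check of rules against each other, with no plan figure to reproduce.

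**Step 1: Cycle 1.** DLT criteria (synopsis table, or the Table 8 Note) set against the dose-modification tables. Section 9.2.4 says withdraw in every row.

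| Cycle 1 DLT | Dose-modification rule |
|---|---|
| Grade 4 neutropenia | Table 4 (solid tumours): hold to grade 1 or less, resume one level lower |
| Febrile neutropenia | Table 4: hold until resolved, resume one level lower |
| Creatinine above 2 x ULN | Table 5, 2 to 3 x ULN: hold, resume at the same or one lower level |
| Grade 3 bilirubin | Table 6: hold, resume one level lower |
| Grade 4 ALT or AST | Table 6, without bilirubin above 2 x ULN: hold, resume one level lower |
| Grade 3 diarrhoea for 72 hours or more despite optimal treatment | Table 9: hold to grade 1 or less or baseline, resume one level lower |
| QTcF of 500 ms or more | Table 8: hold, resume one level lower; discontinue on recurrence after one reduction |

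The list is illustrative. Grade 2 bilirubin with grade 2 ALT or AST is a DLT, and Table 6 allows resumption while bilirubin is at or below 2 x ULN. A related grade 2 thrombocytopenia that stops dosing for 8 of 28 days leaves 20/28 = 71%, below the 75% dosing criterion and so a DLT; Table 4 then resumes one level lower.

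**Step 2: where the rules agree.** Creatinine above 3 x ULN (Table 5), grade 4 bilirubin (Table 6), grade 3 or 4 visual symptoms (Table 7) and grade 4 gastrointestinal toxicity beyond 24 hours (Table 9) all lead to discontinuation. Hy's law cases stop at once under the DLT table's footnote. Table 10 is headed as applying after Cycle 1, so it does not clash. Section 7.4.5 also ends participation after an interruption of more than 14 days, unless the interruption is unrelated to CB-103, so the conflict concerns patients who recover sooner.

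**Step 3: can the text be reconciled?** If Section 9.2.4 prevailed, Table 8's re-treatment step, its extra ECG monitoring and its recurrence rule could never operate. The separate discontinuation rules for Torsades de Pointes and Hy's law would also be redundant. If the tables prevailed, the DLT line in Section 9.2.4 would need an exception, and it has none. No precedence rule was found.

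**Step 4: after Cycle 1.** Under Section 7.4.4 a late QTcF event is not a DLT and Table 8 governs. Under the Note it is a DLT, and Section 9.2.4 would withdraw the patient. Section 9.2.2, in the same safety plan as the withdrawal list, sends the reader to Section 7.4.4 for DLTs, which favours Table 8.

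**Step 5: effect on the analysis.** The primary endpoint (Section 4.2.1, SAP 2.5) counts DLTs in the first 28-day cycle. The dose-determining set (Section 10.1, SAP 3.2) takes DLTs during Cycle 1. The model (Sections 7.4.3 and 10.5.1.3) estimates the probability of a DLT in the first cycle. A late QTcF event enters none of these as a DLT.

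**Step 6: experience so far.** Section 2.5.6 reports 41 patients by 20 August 2020, no QTc prolongation, and one DLT, a grade 3 GGT rise. GGT has no row in Tables 4, 5, 6, 8 or 9.

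**The case against.** **Safeguards exist.** In Part A, any Cycle 1 dose adjustment needs sponsor approval (Section 7.4.5), so a site cannot reduce the dose and resume on its own. The central ECG laboratory issues alerts at QTcF of 500 ms or more (Section 8.2.3.2), and re-treatment under Table 8 requires resolution and central confirmation. These points stand and lower the risk. They do not say which rule the sponsor should apply, and the approval step covers only Cycle 1 of Part A, while the tables also run throughout Part B.

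**The DLT window is not strictly 28 days elsewhere.** One synopsis criterion, delayed start of Cycle 2, runs to Day 43, and Section 7.4.4's sentence on what the model must consider leaves room for later DLTs. This is fair: the Note is less isolated than it looks. It still extends DLT status without limit, which no other provision does.

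**A reader might infer that the Note by itself forces withdrawal after Cycle 1.** That goes too far, because Section 9.2.2 points to the 28-day definition. The text is unclear, with the better reading being Table 8.

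**A reader might also infer that late QTcF events would distort DLT reporting, since the DLT-only table in SAP 5.7.1 states no window.** SAP 2.1.3 and 2.5 already set the window.

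**Conclusion.** The inconsistency is real and should be corrected. In Cycle 1, Section 9.2.4 requires withdrawal for events after which Section 7.4.5, SAP 2.1.4 and Tables 4, 5, 6, 8 and 9 allow re-treatment. After Cycle 1, one event type is unclear, QTcF of 500 ms or more, and only because of the Note.

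The size is limited. It is a matter of conduct and patient safety, with no effect on the DLT primary endpoint, the dose-determining set or the dose-escalation model. A count of affected criteria would depend on how combined and duration-based criteria are split, and would not measure how many patients are concerned. Nor do the documents show that patients had already met the conflict: the single DLT reported by 20 August 2020 falls outside these tables.

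The conclusion rests on reading the withdrawal list as mandatory, as it is worded, and on there being no precedence rule in the protocol or SAP.

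**What to change.** 1. **Table 8 Note.** Limit it to Cycle 1, for example: *If QTcF of 500 ms or more is observed in Cycle 1, this event is a DLT.* Later events then follow Table 8.
2. **Section 9.2.4.** Change the DLT entry to: *a DLT for which Section 7.4.6.1 requires discontinuation.* This matches Section 7.4.5, SAP 2.1.4 and the tables.
3. **Alternative to item 2.** If the sponsor intends withdrawal after every DLT, remove the re-treatment options for Cycle 1 DLTs from the tables, and align Section 7.4.5 and SAP 2.1.4. The choice is the sponsor's, on safety grounds.

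The cost is wording only, with no new data or analysis. Because withdrawal criteria and dosing rules change, the revision may have to go into a protocol amendment under Section 13.5.1.
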